## 12.2 Randomization

In Period 2 of the study, patients will be randomized to sarilumab or matching placebo. This will be done by our administrative assistant [name]. This will be done using a computer-generated random number. An odd number will be assigned to sarilumab and an even number will be assigned to placebo. Only [name] will be aware of the assignment and she will communicate this directly to the pharmacy. The investigators and patients will remain blinded.

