	
reduced to 40 mg daily by the end of week 3 at the clinician's discretion. Starting at week 4, all patients will begin a scheduled prednisone taper that will take place from week 4 until week 16.
 
Patients will be required to adhere to this tapering protocol. If a violation in the tapering schedule occurs, the patient will be deemed a nonresponder. Patients will be required to fill out a daily steroid diary to clearly document their daily prednisone intake. All attempts will be made to perform a pill count at each visit.
 
During Period 2 of the study (starting at Week 16), the patients that responded in Period 1 will be randomized to withdraw from sarilumab. Patients will be assigned in a blinded, 1:1 fashion to receive either sarilumab 200mg subcutaneously every two weeks or matching placebo.

SAMPLE SIZE	15 patients
STATISTICAL CONSIDERATIONS	
The sample size for Period 1 of the trial of 15 patients was calculated based on the assumption that 80% of the patients will respond to open-label sarilumab, allowing for 12 patients to enroll in the randomized withdrawal Period 2 of the study. The sample size of 12 for Period 2 was calculated based on the assumption that 85% of the placebo group (roughly 5 out of 6) will flare (i.e., require reinitiation of prednisone) over the subsequent 12 weeks compared to 15% (roughly 1 out of 6) in the sarilumab group. This relative hazard of 0.20 gives a power of 80% with an alpha of 0.05 to detect a difference between treatment groups assuming Kaplan-Meier analysis.
 
A sample size of 15 was deemed recruitable at Stanford after searching the Stanford medicine Research data Repository (STARR), which is a clinical data warehouse containing all patients seen at Stanford Hospital and Clinics. A search for patients

between the ages of 18 and 75 who were given the diagnosis code for sarcoidosis on at least two separate occasions within the last year and who are currently on prednisone, yields 200 potential patients. Assuming half of these are coded correctly, and one-third of those truly have glucocorticoid-dependent, refractory disease, that leaves roughly 30 patients to screen, half of which we anticipate will be eligible for, and willing to participate in, the study. Our IRB will allow us to identify specific patients within STARR whom we can contact to determine their interest in the study.

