#### *Safety:*

For the patients treated with sarilumab and concomitant DMARD, a higher incidence of treatment-emergent adverse events (TEAEs), serious adverse events (SAEs), and TEAEs leading to discontinuation were observed in the sarilumab treatment groups compared to the placebo group. The incidence of TEAEs leading to death was similar in sarilumab and placebo groups.

In the placebo-controlled population, compared to the placebo group, higher incidences of TEAEs, SAEs, and TEAEs leading to discontinuation were observed in sarilumab 200 mg q2w or 150 mg q2w + DMARD treatment groups relative to the placebo + DMARD group. These differences were generally attributable to higher rates of the AESIs associated with IL-6 blockade, specifically infections and laboratory abnormalities (including decrease in absolute neutrophil count (ANC) and platelet count, increase in transaminase and lipids) in the sarilumab + DMARD groups.

The observations with regards to adverse event (AE) and laboratory parameters with long-term administration were consistent with what was observed in the placebo-controlled population, and no safety findings were identified as attributable to long-term administration.

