## **2.4 Study Design**

The primary purpose of this study is to evaluate sarilumab in the treatment of sarcoidosis. The first period of this trial, Period 1, is single-arm and open-label, in which all patients will receive sarilumab. The second period, Period 2, is a two-arm, randomized withdrawal study in which half of the patients will receive sarilumab and half will receive matching placebo. Period 2 will be double blind. The primary outcome of the study is designed to evaluate efficacy of sarilumab in the treatment of sarcoidosis.

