## **4. TREATMENT PLAN**

At Screening, vital signs will be obtained, a physical examination performed, and complete medical history obtained. **Routine clinical laboratory tests** (including a chemistry panel, complete blood count, urinalysis, spot urine protein and creatinine, C-reactive protein (CRP), erythrocyte sedimentation rate (ESR), urine pregnancy test), **sarcoidosis-related laboratory tests** (including angiotensin converting enzyme (ACE), total immunoglobulins (IgG), urine calcium, 25-hydroxy vitamin D, and **safety laboratory tests** (including serum pregnancy test for females, HIV test, hepatitis B test, hepatitis C test, and quantiferon test for tuberculosis) will be performed. An electrocardiogram and chest x-ray will also be obtained. At Baseline and Week 16, routine clinical laboratory tests and sarcoidosis-related laboratory tests will be repeated, and in addition the following tests will be performed at Baseline (and only repeated at Week 16 if abnormal at Baseline): pulmonary function tests, chest computed tomography, creatinine kinase (CK), aldolase, and lactate dehydrogenase (LDH). At Week 28, routine clinical laboratory tests and sarcoidosis-related laboratory tests will be repeated. At visits 3-11, vital signs, a physical examination, a medical history, and routine clinical laboratory tests will be obtained, urine pregnancy test for WOCBP. At Baseline, Week 16, and Week 28 the ePOST, global patient VAS, global physician VAS, HAQ, and FACIT-F will be assessed. Also at Baseline, Week 16, and Week 28, eight green

top tubes will be collected and processed for plasma and peripheral blood mononuclear cells, which will be stored at -80°C for future research.

During Period 1 (Baseline through Week 16), all subjects will receive 200mg of sarilumab subcutaneously every two weeks. During Period 2 (Week 16 through Week 28), half of the subjects who responded in Period 1 will receive 200mg of sarilumab subcutaneously every two weeks and half of the subjects will receive matching placebo in a double-blinded fashion.

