## 9. STUDY CALENDAR

	Screen Day -35 to 0	Baseline Day 1	Week 2	Week 4	Week 8	Week 12	Week 16	Week 18	Week 20	Week 24	Week 28	Week 34	ET	Unscheduled visit
Written IC	X													
Randomization		X												
Medical history	X													
Vital signs	X	X	X	X	X	X	X	X	X	X	X	X	X	X
Complete PE	X											X	X	
Limited PE		X	X	X	X	X	X	X	X	X	X			X
ePOST		X					X				X			X
Global VAS patient		X					X				X			X
Global VAS physician		X					X				X			X
FACIT-F and HAQ		X					X				X			X
Routine clinical labs:														
Chemistry panel	X	X	X	X	X	X	X	X	X	X	X	X	X	X
CBC w/diff	X	X	X	X	X	X	X	X	X	X	X	X	X	X
Urinalysis, urine P/C	X	X	X	X	X	X	X	X	X	X	X	X	X	X
ESR, CRP	X	X	X	X	X	X	X	X	X	X	X	X	X	X
Urine pregnancy		X	X	X	X	X	X	X	X	X	X	X	X	X
Sarcoidosis labs:														
ACE level	X	X					X				X			X
Immunoglobulins	X	X					X				X			X
Urine calcium	X	X					X				X			X
25-hydroxy vit D	X	X					X				X			X
Safety labs:														
Serum pregnancy	X													
HIV-1/2 serology	X													
Hepatitis B serology	X													
Hepatitis C serology	X													
QuantiFERON TB	X													
Screening tests:														
EKG	X													
Chest x-ray	X													
Sarcoid-specific tests:														
Pulm Function Test		X					X							
CT chest		X					X							
CK, aldolase, LDH		X					X							
Research labs:														
Plasma		X					X				X			
PBMCs		X					X				X			
Review AEs and meds	X	X	X	X	X	X	X	X	X	X	X	X	X	X
Study drug dispensing		X		X	X	X	X		X	X	X			
Drug accountability			X	X	X	X	X	X	X	X	X			X

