## 12.3 Sample Size

The sample size for Period 1 of the trial of 15 patients was calculated based on the assumption that 80% of the patients will respond to open-label sarilumab, allowing for 12 patients to enroll in the randomized withdrawal Period 2 of the study. The sample size of 12 for Period 2 was calculated based on the assumption that 85% of the placebo group (roughly 5 out of 6) will flare (i.e. require reinitiation of prednisone) over the subsequent 12 weeks compared to 15% (roughly 1 out of 6) in the sarilumab group. This relative hazard of 0.20 gives a power of 80% with an alpha of 0.05 to detect a difference between treatment groups assuming Kaplan-Meier analysis. There is no published data on the use of sarilumab in sarcoidosis on which to base these assumptions. However, a parallel can be drawn between glucocorticoid-dependent sarcoidosis and glucocorticoid-dependent recurrent pericarditis, as they are both inflammatory and refractory to typical treatments. The latter condition has been studied with Anakinra, an interleukin 1 $\beta$  recombinant receptor antagonist [19]. In that study, 21 out of 21 patients (100%) had a complete response in Period 1 and were subsequently randomized to withdrawal during Period 2. In Period 2, 9 out of 10 (90%) patients receiving placebo had disease recurrence compared to 2 out of 11 patients (18%) receiving Anakinra. Although this is a different disease with a drug targeting a different inflammatory cytokine, there is precedent for a dramatic response in diseases like sarcoidosis using drugs like sarilumab. A sample size of 15 was deemed recruitable at Stanford after searching the Stanford medicine Research data Repository (STARR), which is a clinical data warehouse containing all patients seen at Stanford Hospital and Clinics. A search for patients between the ages of 18 and 75 who were given the diagnosis code for sarcoidosis on at least two separate occasions within the last year and who are currently on prednisone, yields 200 potential patients. Assuming half of these are coded correctly, and one-third of those truly have glucocorticoid-dependent, refractory disease, that leaves roughly 30 patients to screen, half of which we anticipate will be eligible for, and willing to participate in, the study. Our IRB will allow us to identify specific patients within STARR whom we can contact to determine their interest in the study.

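### The odd/even rule is simple randomisation and does not secure 6 v 6 among about 12 responders, and the calendar marks randomisation at Day 1 instead of Week 16

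*Combined protocol and SAP*

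**What the plan says.** **Method.** Sections 3.4 and 12.2 use one computer-generated random number per patient: "An odd number will be assigned to sarilumab and an even number will be assigned to placebo". An administrative assistant holds the assignments and passes them to the pharmacy. Neither section mentions blocks, a balanced list, stratification or a limit on imbalance.

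**Intended split.** The Synopsis states "Patients will be assigned in a blinded, 1:1 fashion to receive either sarilumab" or placebo. Section 2.4 says "half of the patients will receive sarilumab and half will receive matching placebo", and Section 4 says "half of the subjects who responded in Period 1 will receive 200mg of sarilumab subcutaneously every two weeks". Section 12.3 sizes Period 2 at 12 patients and describes the arms as sixths: "85% of the placebo group (roughly 5 out of 6) will flare", against about 1 in 6 on sarilumab.

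**Timing.** The Synopsis says "During Period 2 of the study (starting at Week 16), the patients that responded in Period 1 will be randomized to withdraw from sarilumab". Sections 3.4 and 12.2 also place randomisation in Period 2. In the Section 9 calendar, the row "Randomization" has one mark, under Baseline Day 1. Its Week 16 cell is empty.

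**The concern.** Deciding each patient by an odd or even number is a coin flip. Over many patients it settles near one half, but over about 12 it often does not. Period 2 is the only randomised comparison in the trial and about six flares are expected in it, so a poor split weakens the primary analysis and cannot be repaired afterwards.

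The calendar mark is a separate error. Responder status cannot be known on Day 1, when every patient starts open-label sarilumab. Read literally, the table would randomise patients who later prove to be non-responders and never enter Period 2, and that would change who belongs to the intention-to-treat population of Section 12.1.

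**Working it through.** **Inputs.** Period 2 has n = 12, being 80% of 15 (Section 12.3). Flare rates over 12 weeks are 85% on placebo and 15% on sarilumab (Section 12.3). The test is a two-sided log-rank (Section 12.1) at alpha 0.05 (Section 12.3). Exponential flare times and no dropout are assumptions; the plan states neither.

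**The plan's own power figure.** Section 12.3 claims 80% at a relative hazard of 0.20. By Schoenfeld's approximation with equal arms, power = Φ(√(D/4)·|ln HR| − 1.96), where D is the number of events.

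- Expected events at 6:6: D = 6 × 0.85 + 6 × 0.15 = 6.
- HR 0.20, D = 6: Φ(1.225 × 1.609 − 1.96) = 50%.
- HR 0.20, D = 12 (every patient counted as an event): 79.6%.
- The stated flare rates imply HR = ln 0.85 / ln 0.15 = 0.086. With D = 6 this gives 85%.

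So 80% does not follow from HR 0.20 with the expected events. That is a separate matter. What counts here is that the calculation assumes six per arm.

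**Chance of imbalance at n = 12.** The number allocated to sarilumab is Binomial(12, 0.5).

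- P(6:6) = C(12,6)/4096 = 924/4096 = 22.6%.
- P(8:4 or worse, either direction) = 2 × Σ C(12,k)/4096 for k ≤ 4 = 38.8%.
- P(9:3 or worse, either direction) = the same sum for k ≤ 3 = 14.6%.

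**Power by split.** Simulated two-sided log-rank at 85% v 15%, 40,000 runs per split:

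| Sarilumab:placebo | Probability of split | Power |
|---|---|---|
| 2:10 | 1.6% | 15% |
| 3:9 | 5.4% | 60% |
| 4:8 | 12.1% | 64% |
| 5:7 | 19.3% | 70% |
| 6:6 | 22.6% | 76% |
| 7:5 | 19.3% | 79% |
| 8:4 | 12.1% | 79% |
| 9:3 | 5.4% | 72% |
| 10:2 | 1.6% | 71% |

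Weighted by the binomial probabilities, mean power is 72.0%, against 76.5% at 6:6. Placebo-heavy splits average 63.8% and sarilumab-heavy splits 77.7%. The asymptotic log-rank test is somewhat liberal at this size: simulated type I error is about 7% at 6:6 and 8% at 9:3. Part of the apparent power at the extreme splits reflects this.

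**Letting the number of responders vary.** With responders ~ Binomial(15, 0.8), P(exactly 12) = 25% and P(fewer than 12) = 35%.

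| | Odd/even | Blocks of 4 |
|---|---|---|
| Mean power | 72% | 76% |
| Arms differ by 3 or more | 47% | 0% |
| Smaller arm has 3 or fewer | 18% | 0.4% |

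**Predictability of blocks.** The worst case is fixed blocks of 4 with the size and all earlier assignments known. The four positions in a block are guessed correctly with probability 1/2, 2/3, 2/3 and 1, a mean of 2.833/4 = 71% against 50% by chance. The fourth position is always determined and the third one time in three, so 1.333/4 = 33% of assignments are determined.

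**Calendar.** The blank-then-mark pattern of the randomisation row is the same as in rows that correctly begin at Baseline, such as ePOST, pulmonary function and plasma. A table broken in conversion is therefore an unlikely explanation. Every text passage on timing points to Period 2.

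**The case against.** Simple randomisation is valid and unbiased, and 1:1 usually means an allocation ratio. The references to halves and to five or one out of six may be loose description. Strictly, the documents do not exclude a balanced list behind the random number; they only fail to describe one. This stands as a limit on wording: no restriction is described.

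The 39% for 8:4 or worse pools both directions, and sarilumab-heavy 8:4 costs no power. Only about 19% of trials (38.8%/2) would be 4:8 or worse against the placebo-heavy side, and about 7% (14.6%/2) 3:9 or worse. This stands, and it is why the power table is given by direction.

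The average loss is small beside the plan's other uncertainties. If the true relative hazard is 0.20 with 85% flares on placebo, power is about 53% at 6:6 and 49% averaged: the same gap of about 4 points, at a level more than 20 points lower. Fewer responders also cost power that blocking cannot restore (70% at 5:5, 59% at 4:4). The secondary Fisher comparison loses nothing on average (44% at 6:6, 51% over all splits, taking the same 85% and 15% as the rates of not being in remission), because that test is so discrete. All of this limits the weight of the point but does not argue for keeping the coin flip.

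Blocking brings some predictability. Section 2.2 reports "decrease in absolute neutrophil count (ANC) and platelet count, increase in transaminase and lipids" with sarilumab, and the calendar schedules blood counts, chemistry and CRP at every visit with no masking of results stated, so investigators at this single site may be partly unblinded. This is a real cost. Varied, undisclosed block sizes reduce it.

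The calendar error is unlikely to mislead staff, since the text is consistent. It remains a plain contradiction.

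**Conclusion.** Both parts hold. As described, the rule is unrestricted simple randomisation. It meets 1:1 in expectation only and does not secure the planned six per arm. The average cost is about 4 points of power (72% v 76%), given the plan's 85% and 15% flare rates, exponential flare times and no dropout. The stronger reason to change is the tail: with a response rate of 80%, 18% of trials would have an arm of three or fewer patients. This is not fatal, and it introduces no bias, but it is cheaply avoided and should be changed. The Day 1 randomisation mark contradicts the text and needs correcting.

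**What to change.** - **Sections 3.4 and 12.2:** replace the odd/even rule with a permuted-block list generated before the first patient reaches Week 16. Prefer block sizes varying at random between 2 and 4 and not disclosed to investigators; fixed blocks of 4 are simpler but easier to guess. The list should cover all 15 patients in case every one responds. The same assistant and pharmacy can hold it. Arms then stay within two patients of each other for any number of responders; 6:6 is exact only if the blocks are complete at 12.
- **Section 9:** move the randomisation mark from Baseline Day 1 to Week 16.
- **Section 12.1 (optional, for clarity):** state that the primary intention-to-treat population is all patients randomised at Week 16.

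The cost is a few lines of text and a different list generator, with no added staff or patients. The price is the limited predictability described above.

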## 12.3 Sample Size

The sample size for Period 1 of the trial of 15 patients was calculated based on the assumption that 80% of the patients will respond to open-label sarilumab, allowing for 12 patients to enroll in the randomized withdrawal Period 2 of the study. The sample size of 12 for Period 2 was calculated based on the assumption that 85% of the placebo group (roughly 5 out of 6) will flare (i.e. require reinitiation of prednisone) over the subsequent 12 weeks compared to 15% (roughly 1 out of 6) in the sarilumab group. This relative hazard of 0.20 gives a power of 80% with an alpha of 0.05 to detect a difference between treatment groups assuming Kaplan-Meier analysis. There is no published data on the use of sarilumab in sarcoidosis on which to base these assumptions. However, a parallel can be drawn between glucocorticoid-dependent sarcoidosis and glucocorticoid-dependent recurrent pericarditis, as they are both inflammatory and refractory to typical treatments. The latter condition has been studied with Anakinra, an interleukin 1 $\beta$  recombinant receptor antagonist [19]. In that study, 21 out of 21 patients (100%) had a complete response in Period 1 and were subsequently randomized to withdrawal during Period 2. In Period 2, 9 out of 10 (90%) patients receiving placebo had disease recurrence compared to 2 out of 11 patients (18%) receiving Anakinra. Although this is a different disease with a drug targeting a different inflammatory cytokine, there is precedent for a dramatic response in diseases like sarcoidosis using drugs like sarilumab. A sample size of 15 was deemed recruitable at Stanford after searching the Stanford medicine Research data Repository (STARR), which is a clinical data warehouse containing all patients seen at Stanford Hospital and Clinics. A search for patients between the ages of 18 and 75 who were given the diagnosis code for sarcoidosis on at least two separate occasions within the last year and who are currently on prednisone, yields 200 potential patients. Assuming half of these are coded correctly, and one-third of those truly have glucocorticoid-dependent, refractory disease, that leaves roughly 30 patients to screen, half of which we anticipate will be eligible for, and willing to participate in, the study. Our IRB will allow us to identify specific patients within STARR whom we can contact to determine their interest in the study.

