# **12. STATISTICAL CONSIDERATIONS**

## **12.1 Statistical Design**

Patient characteristics including demographics, medical history, and concomitant medications will be summarized. The summaries will be done using descriptive statistics, eg, mean, standard deviation, median, minimum and maximum for quantitative values and counts and percents for qualitative variables.

The primary efficacy analysis of flare-free survival in Period 2 from Week 16 to Week 28 will use the intention-to-treat (ITT) population and will be assessed with Kaplan-Meier methods. **Patients will be considered to have flared in Period 2 if they receive rescue medication including increased glucocorticoids, or if they discontinue the study treatment in order to start a different immunosuppressive therapy.**

For Period 1, secondary endpoint variables will be treated as continuous and the values at Week 16 will be compared to Baseline values using Wilcoxon signed-rank tests. The number of patients in glucocorticoid-free remission at week 16 will be reported. Patients will be considered non-responders in Period 1 if they are unable to complete the glucocorticoid taper, receive rescue medication including increased glucocorticoids, or discontinue the study treatment in order to start a different therapy. For Period 1 secondary efficacy endpoints, non-responders will be included in the analysis only if their prednisone dose is equal to or less than the starting dose and stable for the 4 weeks preceding Week 16. The rationale for this is that patients who flare despite sarilumab therapy might be given high doses of steroids, thus improving their endpoints and falsely attributing the success to sarilumab. As a sensitivity analysis, we will also assess the secondary outcomes using the baseline observation carried forward (BOCF) for those patients deemed non-responders.

For Period 2, time to first flare will be compared using a 2-sided log-rank test. The proportion of patients in glucocorticoid-free remission at week 28 in sarilumab-treated patients compared to placebo controls will be analyzed using a Fisher's exact test. The remaining secondary endpoint variables will be treated as continuous and the values at Week 28 will be compared to Week 16 and to Baseline values using Wilcoxon signed-rank tests. We will not perform any corrections for multiple hypothesis testing due to the exploratory nature of this pilot study which solely aims to generate areas of potential future investigation.

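### The relative hazard of 0.20 in the sample size section is a ratio of flare proportions; the implied hazard ratio is about 0.09 to 0.10, and 80% power is modestly optimistic

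*Combined protocol and SAP*

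**What the plan says.** Section 12.3 expects 15 patients in Period 1 to yield 12 for Period 2: "80% of the patients will respond to open-label sarilumab, allowing for 12 patients to enroll in the randomized withdrawal Period 2". It assumes that 85% of the placebo arm (about 5 of 6) will flare "over the subsequent 12 weeks compared to 15% (roughly 1 out of 6) in the sarilumab group". From these rates it concludes: "This relative hazard of 0.20 gives a power of 80% with an alpha of 0.05 to detect a difference between treatment groups". The synopsis repeats the claim: "This relative hazard of 0.20 gives a power of 80% with an alpha of 0.05". The power is said to assume a Kaplan-Meier analysis, which is an estimator and not a test. The test is named in section 12.1: "For Period 2, time to first flare will be compared using a 2-sided log-rank test".

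No formula, software, event count or dropout allowance is given. Section 12.3 states no sidedness.

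As precedent, section 12.3 cites a withdrawal trial in recurrent pericarditis: "9 out of 10 (90%) patients receiving placebo had disease recurrence compared to 2 out of 11 patients (18%) receiving Anakinra". On allocation, section 12.2 says: "An odd number will be assigned to sarilumab and an even number will be assigned to placebo". It describes no blocking.

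**The concern.** In a time-to-event design, relative hazard means hazard ratio. A ratio of cumulative proportions is close to the hazard ratio only when events are uncommon. When 85% of controls have the event, the two are far apart. The effect size printed here therefore does not match the flare rates it is derived from, and the 80% power cannot be obtained from the sentence as it stands.

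Effect size and power are the statistical justification for 12 randomised patients. A reader who takes 0.20 as a hazard ratio, for example when planning the later work this pilot is meant to inform, would look for about 12 events. The hazard ratio that the rates imply needs 5 to 6.

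**Working it through.** **Inputs.** Section 12.3: flare proportions 85% and 15% (rounded to 5/6 and 1/6), 12 patients, alpha 0.05, stated power 80%. Synopsis: 1:1 allocation. Section 12.1: two-sided log-rank test, Week 16 to Week 28 (12 weeks). Expected events, not stated in the plan: 6 × 0.85 + 6 × 0.15 = 6.

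**1. Source of 0.20.** (1/6)/(5/6) = 0.200. With unrounded percentages, 0.15/0.85 = 0.176.

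**2. Implied hazard ratio.** Under proportional hazards, HR = ln(1 − p_sarilumab)/ln(1 − p_placebo).
- 85% v 15%: ln(0.85)/ln(0.15) = 0.086
- 5/6 v 1/6: ln(5/6)/ln(1/6) = 0.102

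In reverse, a hazard ratio of 0.20 with 85% placebo flares gives 1 − 0.15^0.20 = 31.6% sarilumab flares, about twice the assumed 15%.

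**3. The cited pericarditis trial.** Ratio of proportions: (2/11)/(9/10) = 0.202. Hazard ratio, assuming proportional hazards and equal follow-up: ln(9/11)/ln(0.10) = 0.087. The gap is the same.

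**4. Reproducing the 80%.** Schoenfeld, two-sided 0.05, 1:1: events for 80% power = 4(1.960 + 0.842)²/(ln HR)², and power = Φ(√d·|ln HR|/2 − 1.960) for d events.

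| Hazard ratio | Events needed for 80% | Power at stated d |
|---|---|---|
| 0.20 | 12.12 | 50.4% (d = 6); 56.7% (d = 7); 79.6% (d = 12) |
| 0.102 | 6.01 | 79.9% (d = 6) |
| 0.086 | 5.20 | 85.3% (d = 6) |

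Two routes reproduce 80%. One is HR 0.20 with all 12 patients flaring, which contradicts the assumed rates. The other is HR 0.102 with 6 events, which contradicts the stated 0.20. The documents do not show which was used.

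**5. Power of the planned test.** With about 6 events and so extreme a hazard ratio, a large-sample formula is unreliable, so the two-sided log-rank test was simulated directly. Assumptions: exponential flare times, censoring at 12 weeks, no dropout. The first two rows rest on 200,000 runs at 6:6 and on separate runs for random numbers; the third row gives the range over two sets of runs.

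| Scenario | 85% v 15% | 5/6 v 1/6 | HR 0.20, 85% placebo flares |
|---|---|---|---|
| Exactly 6:6 | 76.4% | 71.0% | 53.0% |
| Binomial(15, 0.8) responders, unrestricted odd/even allocation | 72.1% | 66.9% | 49.4% |
| 6:6, flares recorded only at Weeks 18, 20, 24, 28 | 75.3% | 69.0–69.8% | 51.5–52.4% |

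The third scenario has 6 × 0.85 + 6 × 0.316 = 7.0 expected events. A cross-check at 6:6 with a standard package's log-rank routine (4,000 runs) gave 77.2%, 70.3% and 53.7%.

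**6. Number randomised.** For Binomial(15, 0.8): P(fewer than 12) = 0.352, P(exactly 12) = 0.250, P(more than 12) = 0.398.

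**The case against.** The strongest reply is that 80% is not an arithmetic error. A standard formula applied to the plan's own rounded rates gives 79.9%, so the 4 to 9 point gap is one of formula against simulation in a very small trial. That stands, and it is why the shortfall is called modest. It does not rescue the 0.20, which is not the hazard ratio that gives 79.9%.

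Second, the replacement power also depends on method. An exact permutation log-rank test gives 63% and 59% for the two pairs of rates. The asymptotic test does not always hold its level here: with both arms at 85% flares it rejects 7.1% of the time (about 5% with both at 50%). Hazards may not be proportional after withdrawal; keeping the 12-week proportions but placing flares early, uniformly or late moved power between 61% and 79%. This is fair. It is a reason to print the assumptions beside the figure, and none of these variants reaches 80%. A one-sided 0.05 test would (87% and 83%), but section 12.1 specifies two sides.

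Third, a true hazard ratio of 0.20 is hypothetical, because the plan assumes 15% sarilumab flares and not 32%. That is correct. The figure of about 50% describes what the printed label would mean and not what the rates mean.

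Fourth, responder numbers and allocation are separate matters. The synopsis says 1:1, and section 12.2 neither describes nor excludes balancing. The 67% to 72% range is therefore conditional on no balancing and independent responses.

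Finally, this is an exploratory pilot, with no published sarcoidosis data behind its rates and a size also argued from feasibility. That limits the consequence but does not make the stated effect size correct.

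**Conclusion.** The point holds. The mislabelling is certain: 0.20 is the ratio of the rounded flare proportions, and the hazard ratio they imply is 0.086 to 0.102. This rests on proportional hazards alone.

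The stated power is modestly too high for the planned test: 71% to 76% at 6:6, or about 67% to 72% with random responder numbers and unrestricted allocation. These figures assume exponential flare times, no dropout and the asymptotic two-sided log-rank test. If the printed 0.20 were taken as the design hazard ratio with 85% placebo flares, the overstatement would be large, with power near 50%.

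This should be corrected, but it does not undermine the design.

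**What to change.** In section 12.3 and the synopsis:

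- Replace the relative hazard of 0.20 with one consistent pair: a hazard ratio of about 0.09 (85% v 15%; ratio of proportions 0.18), or a hazard ratio of about 0.10 (5/6 v 1/6; ratio of proportions 0.20).
- Give the expected number of flares, about 6.
- Restate power as about 71% to 76% at 6:6; about 67% to 72% allowing for random responder numbers and allocation; and about 50% if the true hazard ratio is 0.20 with 85% placebo flares.
- State the method and assumptions: simulated two-sided log-rank test, alpha 0.05, exponential flare times (proportional hazards), censoring at 12 weeks, no dropout.
- Say that 12 randomised patients is an expected number, with a 35% chance of fewer and a 40% chance of more.

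The cost is wording in two paragraphs. The only downside is a less favourable stated power. No extra patients are asked for, because the study is declared an exploratory pilot and its size also rests on what one site can recruit. For scale, 7 per arm would give 83% (85% v 15%) or 78% (5/6 v 1/6) under the same simulation assumptions.
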